## Exposure of this drug

Using the SAS, exposure of this drug will be summarized with respect to the following aspects:

- Duration of treatment [<52 weeks, ≥52 to <78 weeks, ≥78 to <104 weeks, ≥104 to <156 weeks, ≥156 weeks]

- − Initial daily dose [<20 mg, 20mg, ≥20 mg]
- Total number of treatment weeks (continuous, non-dosing periods excluded, unit: weeks)
- Total dose administered (continuous)

The duration of treatment is defined as the length of the time from the date of first dose to the last dose in this study, including non-dosing periods. If the patient remains on the treatment at the end of observation period, the duration of treatment will have the value ">156 weeks".

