## 2.1. Study design

Target patients

All patients who received/used this drug will be targeted in this study.

Dosage and administration

The usual adult dosage for oral use is 20 mg of tafamidis meglumine once daily.

Observation period

3 years from the first day of treatment with this drug (156 weeks)

However, the observation period for patients who started to receive this drug after May 2018 will be 1.5 years (78 weeks).

Major investigation items

Hepatotoxicity should be evaluated in this study as a major investigation item and, if information on hepatotoxicity is obtained, it will be separately investigated in detail.

[Rationale for setting]

Although necrosis and hypertrophy of hepatocytes were observed in the repeated-dose toxicity study in mice, since the Japanese clinical data at the time of approval application are limited, hepatotoxicity was set as the major investigation item in this study to confirm the post-marketing safety profile.

Study size and its rationale

[Planned sample size]

All patients who received/used this drug will be targeted in this study.

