## [Rationale for sample size]

On the basis of the review of data on patients with familial amyloid polyneuropathy who were registered in the database from the Amyloidosis Clinical Survey Forms of the Specific Diseases Treatment Research Program by the Ministry of Health, Labour and Welfare for 3 years from 2003 to 2005, it is reported that the number of patients with familial amyloid polyneuropathy is 64 to 88 patients/year, and the estimated prevalence of familial amyloid polyneuropathy in Japan is 0.87 to 1.1 per population of 1 million people after the number of patients was corrected and calculated from the acquisition rate of data 1). When this

> PFIZER CONFIDENTIAL Page 13

prevalence is multiplied by the Japanese population (127.54 million, as of November 2012), the estimated number of patients with TTR-FAP (hereinafter referred to as this disease) is approximately 111 to 140. On the website of the Japan Intractable Diseases Information Center, the estimated annual number of patients treated for this disease is approximately 130 on the basis of the nationwide epidemiological survey conducted in 1991. As described above, considering that this disease is a rare disease and the safety and efficacy information of this drug based on Japanese clinical studies are limited, all patients who received/used this drug will be collected as much as possible.

Planned period covered by this study

Duration of study: November 2013 to May 2021 (7.5 years)

Registration period: November 2013 to November 2019 (6 years)

A contract will be concluded after the start date of the study period, and then, the patient registration will be started.

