#### 5.4. Subgroups

Subgroup analyses for safety and efficacy will be performed with respect to the following factors:

- Patient characteristics
  - Sex [male, female]
  - Age [ $<15 \text{ yrs.}, \ge 15 \text{ to } <65 \text{ yrs.}, \ge 65 \text{ yrs.}$ ]
  - Body weight [ $\leq 50 \text{ kg}$ ,  $\geq 50 \text{ to } \leq 60 \text{ kg}$ ,  $\geq 60 \text{ kg}$ ]
  - BMI [<18.5, ≥18.5 to <25.0, ≥25]
  - Onset age [ $\leq 50$  yrs.]  $\geq 50$  yrs.]
  - Duration of disease [ $\leq 5$  yrs.]  $\geq 5$  yrs.]
  - Past treatment with this drug [present, absent]
  - Mutant genotype 2 [with V30M, without V30M]

- Karnofsky performance status [100-80, 70-50, 40-10]
- Family history of TTR-FAP [present, absent]
- Origin of patient [endemic region, non-endemic region]
- Past history of organ transplantation [present, absent]
- Past history of liver transplantation (including for purposes other than the treatment of target disease) [present (including domino liver transplantation), absent] \* Only for safety assessment
- Past history of liver transplantation other than domino liver transplantation [present, absent (including domino liver transplantation)] \* Only for efficacy assessment
- Hepatic impairment [present, absent]
- Hepatic impairment [absent, mild, moderate, severe]
- Renal impairment [present, absent]
- Baseline total NIS score [ $\leq 70$ ,  $\geq 70$ ]
- Baseline NIS-LL score [ $\leq 10$ , >10 to  $\leq 20$ , >20]
- Baseline total QOL (TQOL) score [ $\leq 20$ , >20 to  $\leq 40$ , >40]
- Severity of disease [Stage 1 (walking ability score 0-2), Stage 2 (walking ability score 3a/3b),
   Stage 3 (walking ability score 4)]

Subgroup analysis for mutant genotype will be performed only in patients with a diagnosis of mutant genotype.

- Others
  - Pretreatment (loperamide) [present, absent]
  - Pretreatment (prednisolone) [present, absent]
  - Pretreatment (rosuvastatin) [present, absent]
  - Pretreatment (NSAIDs) [present, absent]
  - Duration of treatment [ $\leq 52$  weeks, >52 to  $\leq 104$  weeks, >104 to  $\leq 156$  weeks, >156 weeks]
  - Concomitant medication (loperamide) [present, absent]
  - Concomitant medication (prednisolone) [present, absent]
  - Concomitant medication (rosuvastatin) [present, absent]
  - Concomitant medication (NSAIDs) [present, absent]

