#### 8.2. Statistical Analyses

#### 8.2.1. Description of patients

#### **Combination clinical practice**

Given the nature of this disease as a rare disease, patients may be treated (or receive prescriptions of this drug) at multiple sites during the observation period (combination clinical practice). For possible patients

PFIZER CONFIDENTIAL Page 23 with combination clinical practice, identification will be determined at a case conference using information on birthdate, sex, mutant genotype, and names of combination practice sites or sites after patient transfer. In principle, data at the site with earlier date of treatment initiation will be adopted for the analysis of patient characteristics. All data after the start of treatment for an identical patient will be combined and handled using this start date of treatment as the origin (data linkage).

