## Constitution

Using the set of all registered patients, the numbers of registered patients, CRF-collected patients, patients after data linkage, patients included in safety analysis, and patients included in efficacy analysis will be determined. Using the SAS, the number of patients included in the safety analysis will be determined for each planned observation time (Weeks 78 and 156). In addition, CRF-uncollected patients, patients excluded from the safety analysis, and patients excluded from the safety analysis will be counted as a total and by reason for exclusion.

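### SAP 8.2.2 sets treatment duration to >156 weeks for every patient still on drug at the end of observation, so patients on the 78-week schedule are counted as three-year exposures

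*SAP*

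**What the plan says.** SAP 8.2.2 defines duration of treatment as "the length of the time from the date of first dose to the last dose in this study", with non-dosing periods included. It tabulates duration in five classes: <52, ≥52 to <78, ≥78 to <104, ≥104 to <156 and ≥156 weeks. The next sentence overrides the definition for one group: "If the patient remains on the treatment at the end of observation period, the duration of treatment will have the value" >156 weeks.

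The observation period has two lengths. The standard is 156 weeks, but SAP 2.1 and Protocol 7.2.4 both add that "the observation period for patients who started to receive this drug after May 2018 will be 1.5 years (78 weeks". Such patients can enter because registration stayed open well past that date: "Registration period: November 2013 to November 2019 (6 years".

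Two other provisions bear on the point:
- SAP 8.2.1 (Constitution) recognises both schedules: "the number of patients included in the safety analysis will be determined for each planned observation time (Weeks 78 and 156". That applies to patient counts only.
- SAP 8.2.1 (Combination clinical practice) says that data for one patient treated at several sites "will be combined and handled using this start date of treatment as the origin (data linkage", so a patient's origin can be earlier than the start at the reporting site.

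**The concern.** The override is harmless if observation always lasts 156 weeks. It stops being harmless once some patients are observed for 78. For a late starter still on drug at Week 78, two adjacent sentences of SAP 8.2.2 give two different answers, and those answers fall in different classes of the same table.

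The study exists to describe safety and efficacy in long-term use (SAP 2.2), and the final analysis supports the reexamination application (SAP 3). The table shows readers how much three-year experience lies behind the results. The error runs in one direction: it adds patients to the longest class and removes them from ≥78 to <104 weeks.

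**Working it through.** **Inputs from the documents**
- Observation period: 156 weeks, or 78 weeks for starts after May 2018 (SAP 2.1, Protocol 7.2.4).
- Registration to November 2019; study ends May 2021 (SAP 2.1, Protocol 7.2.2).
- Duration definition, override and classes (SAP 8.2.2).
- Not given: the number of patients on the 78-week schedule, and the share on either schedule still on drug at the end.

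**Step 1. Apply the rule and the definition to the same patients** (no linkage; Weeks 120 and 60 are example stopping times)

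| Schedule and status | Override as written | First dose to last dose |
|---|---|---|
| 156 weeks, on drug at Week 156 | ≥156 | ≥156 |
| 156 weeks, stopped at Week 120 | ≥104 to <156 | ≥104 to <156 |
| 78 weeks, stopped at Week 60 | ≥52 to <78 | ≥52 to <78 |
| 78 weeks, on drug at Week 78 | **≥156** | **≥78 to <104** |

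The rule reproduces the definition in the first three rows. It fails only in the last.

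**Step 2. Look for a limiting passage.** The Weeks 78 and 156 split in SAP 8.2.1 covers patient counts. The completer rule at ≥156 weeks (SAP 8.2.1, Discontinuation and dropouts) governs the discontinuation table. Neither restricts the override.

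**Step 3. Check the calendar.** Take after May 2018 as 1 June 2018 onward and the study end as 31 May 2021.
- Start on 1 June 2018: 1,095 days / 7 = 156.4 weeks to the study end.
- Start on 30 November 2019: 548 days / 7 = 78.3 weeks.

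Without an earlier linked origin, only patients starting in the first days of June 2018 could have passed 156 weeks even by the end of the whole study. Their own observation stops at 78 weeks.

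**Step 4. Error per patient.** 156 − 78 = 78 weeks if the last recorded dose is at Week 78. Protocol 7.2.4 places the final assessment at the first visit on or after the end date, so a later last dose may be recorded. At Week 82, for example, the gap is 156 − 82 = 74 weeks. An earlier linked origin shrinks it further.

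**Step 5. Effect on the top class (illustrative).** Let N be the patients analysed, p the share on the 78-week schedule, and r the share still on drug at the end of observation, assumed equal on both schedules.
- Correct count in the top class: N(1 − p)r
- Patients wrongly added: Npr
- Relative inflation: Npr / [N(1 − p)r] = p/(1 − p)

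| Assumed p | p/(1 − p) |
|---|---|
| 5% | 0.05/0.95 = 5.3% |
| 10% | 0.10/0.90 = 11.1% |
| 25% | 0.25/0.75 = 33.3% |

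The 25% row corresponds to even accrual: June 2018 to November 2019 is 18 months, and 18/72 = 25% of the six-year registration period. The documents do not say accrual was even. If retention differs by schedule, the result is multiplied by the ratio of the two retention shares.

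**The case against.** The strongest reply is that the sentence is left over from the 156-week schedule. The revision history shows 78-week cut points being added to the duration classes, which gives a 78-week completer an obvious place, and a sensible programmer would use it. The table is descriptive, and the SAP has no hypotheses or decision rules. Total treatment weeks and total dose are reported separately. A top class larger than the Week 156 cohort would be noticed. This limits the consequence, but it does not make the instruction correct, and the analysis should not depend on someone overriding an explicit rule. Nor would an inflated top class necessarily exceed the Week 156 cohort, because some patients on that schedule will have stopped early.

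The reply is right about several stronger readings that a reader might infer:
- **Every affected patient is overstated by at least 78 weeks.** Not supported. The last recorded dose can fall after Week 78, and linkage can move the origin earlier. A patient who started at a second site after May 2018 may truly have more than 156 linked weeks.
- **The top class is inflated by a known amount.** Not supported. No document gives p or retention. This is an all-cases survey including retrospective cases, in a disease with an estimated 111 to 140 patients, begun two months after approval. Early enrolment of existing patients is at least as plausible as even accrual, and would make p smaller than 25%.
- **Other analyses are wrong too.** Not supported. Section 5.4 has a duration factor with a top class ("weeks, >156 weeks"), but the SAP does not say that it uses this derivation. The override is not applied to total treatment weeks or total dose, and the onset-timing denominators in 8.2.3.1 are described separately.

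**Conclusion.** The point holds on the text as written. SAP 8.2.2 places patients on the 78-week schedule who are still on drug at Week 78 in the ≥156 weeks class. Its own definition places them in ≥78 to <104 weeks, unless linked data show longer treatment. The number with three years of observed treatment is overstated.

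The misclassification follows from the documents alone. The size per patient is roughly 78 weeks, subject to the two exceptions above. Because duration is shown only in classes, the harm is a wrong class count, not a distorted mean or total. The effect on the class, about 5% to 33%, rests on assumed late-starter shares of 5% to 25% and equal retention, and should be read as an illustration. Any effect on the Section 5.4 subgroups is conditional on that factor using the same variable.

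This is a correction worth making to a descriptive table that bears directly on the study's stated purpose. It does not threaten the study's other results.

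**What to change.** Replace the override sentence in SAP 8.2.2 with:

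> If the patient remains on treatment at the end of the observation period and has at least 156 weeks of observed or linked follow-up from first dose, the duration of treatment will have the value >156 weeks. For any other patient remaining on treatment at the end of the observation period, the observed duration from first dose (linked origin where applicable) to the end of observation is used.

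Keep the value >156 weeks; do not substitute ≥156 weeks. Section 5.4 has no ≥156 weeks class, so a completer counted to exactly Week 156 would drop into its >104 to ≤156 weeks class. With >156 weeks kept, 156-week completers still on drug map to the top class in both sections. A 78-week completer without earlier linked treatment falls in ≥78 to <104 weeks in 8.2.2 and, if the variable is shared, in >52 to ≤104 weeks in 5.4. The SAP should state whether the Section 5.4 factor uses this variable; if it does, the same correction carries over.

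The cost is two sentences and a small change to the derivation, using data already collected. The count of three-year exposures may fall. A footnote marking treatment as ongoing at the end of observation, and a split of the table by planned observation time, would help readers but are optional.

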## 8.2.3. Safety analysis

Using the SAS, the following safety analyses will be performed:

#### 8.2.3.1. Adverse reactions

#### All adverse reactions

Adverse reactions will be summarized by SOC and PT in terms of n and proportion.

In particular, important potential risks, i.e., events related to hepatotoxicity, hypersensitivity reaction, developmental and reproductive toxicity, and infections will be summarized for each event in terms of n and proportion; when n is very small for each event, however, only a listing will be presented in tabular form.

In addition, each of events related to pain in extremity, myalgia, gastrointestinal symptoms, skin, central nervous system, fall, suicide, hepatopathy, thyroid function, vitamin A deficiency, and increased blood glucose will be summarized separately in terms of n and proportion, as necessary.

#### Serious adverse reactions

Serious adverse reactions will be summarized by SOC and PT in terms of n and proportion.

#### **Details of adverse reactions**

Adverse reactions will be summarized in terms of n and proportion by each of the following factors:

- Seriousness [serious, non-serious]
- Known/unknown [known, unknown]
- Action taken [permanent discontinuation, temporary discontinuation or dose reduction, dose increase or no change]
- Outcome [not recovered, recovered with sequelae, improved, resolved/recovered, unknown]

Multiple adverse reactions of the same PT occurring in the same patient will be handled as follows:

- Seriousness: If both serious and non-serious reactions of the same PT occurred in the same patient, the patient will be counted as one with serious reaction.
- Known/unknown: If both known and unknown reactions of the same PT occurred in the same patient, the patient will be counted as one with unknown reaction.
- Action taken: If multiple actions were taken for adverse reactions of the same PT, only one category of action will be adopted with "permanent discontinuation", "temporary discontinuation or dose reduction", and "dose increase or no change" being given priority in this order.
- Outcome: The outcome for the last event will be adopted.

#### Major investigation items

For each of the following major investigation items, patients who experienced relevant events will be summarized in terms of n and proportion:

- Hepatotoxicity

In addition, patients who experienced each major investigation item will be summarized by action taken and outcome for each SOC and PT.

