7.3.2.8. Tests/clinical laboratory tests

For the following test items conducted from the first day of treatment with this drug until the end of the observation period (or date of discontinuation of treatment with this drug), enter the test dates (dates of measurement) and test results. For the tests conducted before the start of treatment with this drug, enter the test results immediately before the first day of treatment (including the first day of treatment). For clinically significant fluctuations compared to those before the start of treatment with this drug, enter the details in the adverse event column.

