7.3.2.8.1. Clinical laboratory tests

(1) Hematology: White blood cell count, neutrophil count, lymphocyte count, red blood cell count, platelet count, hemoglobin, prothrombin time

(2) Biochemistry: AST (GOT), ALT (GPT), AL-P, LDH, γ -GTP, total bilirubin, triglycerides, serum creatinine, serum albumin

(3) Endocrine test: Thyroid-stimulating hormone (TSH), total T4, free thyroxine (FT4)

(4) Urinalysis: Urine protein (qualitative)

Pfizer Confidential Page 17 of 37

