7.3.2.12. Adverse events

Occurrence of adverse events (AEs) from the start date of administration of this drug to the end date of observation period should be confirmed and the following information should be recorded. If any AE is

observed, the investigator will take appropriate measures, promptly report it to Pfizer, and in principle, transcribe and confirm the course until the symptom disappears.

Also, further investigation should be separately conducted, if deemed necessary by Sponsor for patients who experienced a serious adverse reaction, an unexpected adverse reaction or other adverse reactions not listed in the package insert.

- (1) Presence/absence of AE
- (2) Name of AE
- (3) Date of occurrence
- (4) Intervention
- (5) Seriousness
- (6) Outcome
- (7) Causal relationship to this drug

If the AE is associated with abnormal laboratory values, i.e., clinical laboratory tests, the following information should also be recorded:

- (1) Laboratory parameter
- (2) Site reference value
- (3) Unit
- (4) Date measured
- (5) Results

Note: AEs are any and all unfavorable events (including clinically significant abnormal changes in laboratory tests) occurring in patients after starting the targeted drug treatment regardless of their causal relationship. Serious adverse events (SAEs) are any unfavorable medical occurrences that result in death, are life-threatening, require (or prolong) hospitalization, cause persistent or significant disability/incapacity, result in congenital anomalies or birth defects, or are other conditions which represent significant health hazards.

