9.4. Definitions of safety events

9.4.1. Adverse events

An AE is any untoward medical occurrence in a patient administered a medicinal product. The event need not necessarily have a causal relationship with the product treatment or usage. Examples of AEs include but are not limited to:

- Abnormal test findings (see below for circumstances in which an abnormal test finding constitutes an AE);
- Clinically significant signs and symptoms;
- Changes in physical examination findings;
- Hypersensitivity;
- Progression/worsening of underlying disease;

- Lack of efficacy;
- Drug abuse;
- Drug dependency;

Additionally, for medicinal products, they may include the signs or symptoms resulting from:

- Drug overdose;
- Drug withdrawal;
- Drug misuse;
- Off-label use;
- Drug interactions;
- Extravasation;
- EDP;
- Exposure during breastfeeding;
- Medication error;
- Occupational Exposure.

Abnormal test findings

The criteria for determining whether an abnormal objective test finding should be reported as an AE are as follows:

- Test result is associated with accompanying symptoms, and/or
- Test result requires additional diagnostic testing or medical/surgical intervention, and/or
- Test result leads to a change in study dosing or discontinuation from the study, significant additional concomitant drug treatment, or other therapy, and/or
- Test result is considered to be an AE by the investigator or Pfizer.

Merely repeating an abnormal test, in the absence of any of the above conditions, does not constitute an AE. Any abnormal test result that is determined to be an error does not require reporting as an AE.

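### In the legible text, hepatotoxicity is counted only from entered adverse events; the liver tests already collected should cross-check that count and show how many patients were tested

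*SAP*

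**What the plan says.** **Analysis.** Protocol 7.3.2.14 and SAP 6.1 name one major investigation item, hepatotoxicity. It was chosen because of liver-cell findings in a mouse toxicity study and limited Japanese data. In SAP 8.2.3.1, under Major investigation items, "patients who experienced relevant events will be summarized in terms of n and proportion", with a further breakdown by action taken and outcome. SAP 6.1 leaves the choice of qualifying events to a separate document.

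**Collection.** The instruction in Protocol 7.3.2.8 to enter test dates and results begins "For the following test items conducted from the first day of treatment with this drug until the end of the observation period". It also asks for the last result before treatment. Protocol 7.3.2.8.1 lists "Biochemistry: AST (GOT), ALT (GPT), AL-P, LDH", followed by gamma-GTP and total bilirubin among others.

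**Route from a laboratory value to an adverse event.**
- Protocol 7.3.2.8: "For clinically significant fluctuations compared to those before the start of treatment with this drug, enter the details in the adverse event column".
- The note in Protocol 7.3.2.12 defines adverse events as "including clinically significant abnormal changes in laboratory tests".
- Protocol 9.4.1 gives alternative criteria: symptoms; further diagnostic testing or intervention; a change in dosing, discontinuation or significant other treatment; or the investigator or sponsor considering the result an adverse event. It adds: "Merely repeating an abnormal test, in the absence of any of the above conditions, does not constitute an AE".
- Protocol 7.3.2.12: "If the AE is associated with abnormal laboratory values, i.e., clinical laboratory tests, the following information should also be recorded". The site reference value is among those items.

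**The concern.** Routine enzymes and bilirubin are the most direct measurements of liver effect in this database. If the study's one major safety question is answered only from what sites chose to enter as events, the answer depends on each physician's view of clinical significance. Asymptomatic rises could sit in the laboratory pages and never enter the hepatotoxicity table.

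A second problem concerns reading the result. Tests are recorded as they occur in routine care, with no fixed schedule. A zero or low count could mean that few patients had liver effects, that few were tested on treatment, or that few rises were entered. The legible plan gives no means of telling these apart. The risk is false reassurance on the item the study was asked to examine most closely.

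**Working it through.** **1. Where the collected liver tests could be used.** Each place that might hold a laboratory analysis was checked.

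| Place | Legible content on liver tests |
|---|---|
| Protocol 7.7 | Major safety analysis is adverse-reaction incidence |
| SAP 6.1 | Adverse reactions, adverse events, serious events, hepatotoxicity events; no laboratory endpoint |
| SAP 7 | No rule for laboratory values |
| SAP 8.2.3.1 to 8.2.3.3 | Counts of reactions and events only, including the conditional subgroup analysis of hepatotoxicity |
| SAP 9 | Event listings for the major item; no laboratory listing |
| SAP Appendix 1 | Windows for efficacy endpoints and physical symptoms; none for liver tests |

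Serum albumin does have a legible analysis, but only as a component of mBMI, an efficacy endpoint.

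**2. How a raised value reaches the count.** It must be judged clinically significant (7.3.2.8, 7.3.2.12) or meet a 9.4.1 criterion. It must then be entered, and it must match the separate event definition. None of the legible steps has a numeric threshold. A definition document that includes terms such as raised ALT would still select only from entered events. The Major investigation items paragraph also sits under Adverse reactions, so the count may be confined to events judged related. The all-causality table in 8.2.3.2 partly offsets that, but it is event-based too.

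**3. Whether anything checks the step.** Protocol 7.3.2.15 has the investigator confirm that hepatotoxicity events have been entered. It does not ask for a comparison with the laboratory results.

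**4. The denominator.** SAP 5.1 excludes patients with no adverse-event information. Nothing legible counts patients with no on-treatment liver test.

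**5. Illustration of size.** The only cohort-size basis in the documents is prevalence times population (Protocol 7.5.2): 0.87 × 127.54 = 110.96 and 1.1 × 127.54 = 140.29, which reproduces the stated 111 to 140. Let *p* be the proportion of patients with a notable rise in the laboratory data and *c* the share of those entered as events. Both are assumed; neither is in the documents. Expected counted cases = *N* × *p* × *c*. The chance of counting at least one = 1 − (1 − *pc*)^*N*.

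| *p* | *c* | Expected, *N* = 111 to 140 | Chance of at least one |
|---|---|---|---|
| 5% | 100% | 5.6 to 7.0 | over 99% |
| 5% | 50% | 2.8 to 3.5 | 94% to 97% |
| 5% | 25% | 1.4 to 1.8 | 75% to 83% |
| 2% | 100% | 2.2 to 2.8 | 89% to 94% |
| 2% | 50% | 1.1 to 1.4 | 67% to 76% |
| 2% | 25% | 0.6 to 0.7 | 43% to 50% |

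With a cohort this small, incomplete entry could decide whether the table shows any case at all.

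**The case against.** **Redaction.** SAP 6.3, 8.2.5 and a block between 8.2.3.3 and 8.2.4 are blacked out, and the last is where a further safety subsection could fall. The SAP revision history shows that material once in 6.1 and 8.2.3 was moved to 6.3 and 8.2.5. A reader might infer that no laboratory analysis is planned at all; the documents do not support that. On the other side, the material moved there, the physical-symptom assessments, remains visible in Appendix 1 and Section 9, and liver tests appear in neither. This makes a hidden analysis less likely but does not exclude one. The missing windows prove little by themselves, because a worst-value table needs none.

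**The entry rules.** A reader might infer that 7.3.2.8 and 9.4.1 contradict each other, or that 9.4.1 shuts out a large asymptomatic rise that is merely rechecked. Neither follows. The 9.4.1 criteria are alternatives, and one is that the investigator or sponsor considers the result an adverse event. A change judged clinically significant therefore qualifies under both sections. What stands is narrower: entry turns on judgement without a number.

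**Existing safeguards.** Besides the check in 7.3.2.15, 7.3.2.14 promises detailed investigation of hepatotoxicity information, and the sponsor can query CRFs (7.6.5.2). These reduce under-entry. No legible text makes any of them a systematic comparison of laboratory values with entered events.

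**Nature of the study.** This is a descriptive survey with no hypotheses; the SAP follows the protocol's stated safety analysis, and Protocol 7.9 already warns of missing data. That limits the weight of the point, but a general warning does not tell the reader how many patients were tested.

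**Conclusion.** The point holds as a worthwhile, inexpensive improvement. In the legible text, the sole major investigation item is counted only from entered events, while dated liver tests with a pre-treatment value go unused for safety. Some asymptomatic rises can therefore go uncounted, and a low count cannot be interpreted without the number tested.

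The size is unknown. The illustration rests on assumed frequencies of rises and of entry. It also treats every patient as tested and uses a prevalence estimate in place of the number actually registered over six years. A reader might also be tempted to attach an upper confidence limit to a zero count and inflate it for untested patients. The documents do not support that as a measure of this problem: the plan commits to no interval for this proportion, the testing rate is not given, and such a limit says nothing about rises recorded but not entered.

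The conclusion is conditional on the redacted sections holding no laboratory analysis.

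**What to change.** If a redacted section already analyses the liver tests, add a cross-reference to it in SAP 8.2.3. Otherwise add two outputs there, on the safety analysis set:

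1. **A descriptive liver-test table.** Give the number of patients with at least one on-treatment ALT or AST result and with at least one on-treatment bilirubin result. Take each patient's worst on-treatment AST, ALT, AL-P and bilirubin as a multiple of the pre-treatment value and, as an approximation, of one pre-stated common upper reference limit. Present these in pre-stated categories, overall and by baseline hepatic impairment and liver-transplant history.
2. **A listing** of patients above a pre-stated level, showing for each whether a hepatotoxicity adverse event was recorded.

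The cost is SAP wording, one table and one listing from data already held. The protocol planned data collection to end in May 2021 and the latest SAP version is dated March 2023, so the change belongs in the analysis and not in the entry rules.

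There are two drawbacks. Testing follows routine care, so patients tested more often have more chances to show a high value. A common limit is only approximate, because site reference values are requested only for tests linked to adverse events.
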